6.3. Exploratory Analysis of HBV Endpoints in Virally Suppressed CHB Participants (Phase 1b)

An 8-number summary of quantitative HBeAg (IU/mL) and change from baseline by visit will be summarized by treatment group for virally suppressed CHB participants in the FAS who were HBeAg positive at baseline (and had HBeAg quantitative data collected) by treatment group for participants in cohorts 5, 6, and 7. Listings will include all data collected for quantitative HBeAg regardless of the participant's HBeAg status at baseline.

Listings of HBV serology results and HBV DNA will be provided for virally suppressed CHB participants.

6.3.1. Maximum Postbaseline Decrease from Baseline in HBsAg (\log_{10} IU/mL)

The baseline value and lowest change from baseline value after study Day 1 for each participant will be summarized for virally suppressed CHB participants assigned to active treatment within each cohort (5, 6, and 7), and all CHB participants assigned to placebo using an 8-number summary.

Maximum Postbaseline Decrease from Baseline in HBsAg (\log_{10} IU/mL) is calculated as:

(Lowest change from baseline value after Day 1 for HBsAg [\log_{10} IU/mL]) $\times -1$

The maximum postbaseline decrease from baseline in HBsAg (\log_{10}) for each participant will be used to classify the participant's best HBsAg (\log_{10} IU/mL) response: ≥ 1 \log_{10} decrease from baseline; 0.5 to < 1.0 \log_{10} decrease from baseline, < 0.5 \log_{10} IU/mL decrease from baseline.

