1.1. Study Objectives and Endpoints

Primary Objective	Primary Endpoint

 To evaluate the safety and tolerability of repeated dosing of GS-2829 and GS-6779 in healthy participants and in virally suppressed participants with CHB 	
 Proportion of participants with treatment-emergent AEs, SAEs, and laboratory abnormalities
Secondary Objective	Secondary Endpoints

 To evaluate the immunogenicity of repeated dosing of GS-2829 and GS-6779 in healthy participants and in virally suppressed participants with CHB 	
 Incidence and magnitude of vaccine-induced T-cell responses
Exploratory Objectives	Exploratory Endpoints

 To evaluate the impact of GS-2829 and GS-6779 on HBV-specific viral biomarkers in participants with CHB 	
 Change in HBsAg from baseline Proportion of participants with HBsAg loss with or without HBsAg seroconversion Changes in quantitative hepatitis B e antigen (HBeAg) from baseline

Note: Only exploratory objectives to be analyzed under this SAP are included. Exploratory objectives may be analyzed outside of this SAP will not be described here.

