3.8. Visit Definitions

3.8.1. Definition of Baseline, Postbaseline, Study Day, and Follow-Up Day

Baseline is defined as the last available value collected on or prior to the first dose date (and time, where applicable) of investigational product (i.e., prior to taking first dose of investigational product).

Postbaseline is defined as any value collected after the first dose of investigational product.

Study day will be calculated from the first dosing date of investigational product and derived as follows:

- For postdose study days: Assessment Date – First Dosing Date + 1
- For days prior to the first dose: Assessment Date – First Dosing Date

Therefore, study day 1 is the day of first dose of investigational product.

Last Dose Date is defined as the date of the last injection of GS-2829 or GS-6779 [or PBO].

Follow-Up (FU) Day will be calculated from the last dosing date of investigational product and will be derived as follows:

- Assessment date – Last Dose Date

Both Study Day and FU Day will be displayed in listings of data for endpoints remapped to FU visits in Table 3-1 to Table 3-4 in Section 3.8.2 (when possible).

Last Study Date is the latest of clinic visit dates and laboratory visit dates, including all follow-up visits for participants who prematurely discontinued study or who completed study according to the Study Completion eCRF.

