Day 15	Day 15	Day 15 [#]	Day 15 [#]
Day 29	Day 29* ^{\$}	Day 29*# ^{\$}	Day 29*# ^{\$}
Day 43	–	Day 43	Day 43
Day 57	Day 57* ^{\$}	Day 57*# ^{\$}	Day 57*# ^{\$}
Day 71	FU-WK2	Day 71	Day 71
Day 85	FU-WK4^{\$}	Day 85*# ^{\$}	Day 85*# ^{\$}
Day 99	–	FU-WK2	Day 99
Day 113	–	FU-WK4*#^{\$}	Day 113*# ^{\$}
Day 127	–	–	Day 127
Day 141	FU-WK12^{\$}	–	Day 141*# ^{\$}
Day 155	–	–	FU-WK2
Day 169	–	FU-WK12*#^{\$}	FU-WK4*#^{\$}
Day 225	FU-WK24*^{\$}	–	FU-WK12*#^{\$}
Day 253	–	FU-WK24*#[#]	–
Day 309	–	–	FU-WK24*#[#]

*Creatinine Clearance (estimated using Cockcroft-Gault method) collected at this subset of visits.

#Viral biomarkers (HBV DNA, quantitative HBsAg, anti-HBsAg antibody, HBcrAg, HBeAg and anti-HBeAg antibody) collected at this subset of visits for participants in Cohorts 5, 6, and 7 (only).

\$ Antibody to HBsAg [Phase 1a participants only].

Table 3-2. Remapped Follow-Up Visits for Vital Signs, Weight, and BMI

Nominal Visit	Cohorts 1, 2	Cohorts 3, 4, 5, 6	Cohorts 7, 8
Last Value prior to first dose date=Baseline	Baseline*#	Baseline*#	Baseline*#
Day 8	Day 8	–	–
Day 15	Day 15	Day 15	Day 15
Day 29	Day 29	Day 29*#	Day 29*#
Day 43	–	Day 43	Day 43
Day 57	Day 57*#	Day 57*#	Day 57*#
Day 64	FU-WK1	–	–
Day 71	FU-WK2	Day 71	Day 71
Day 85	FU-WK4	Day 85*#	Day 85*#
Day 92	–	FU-WK1	–
Day 99	–	FU-WK2	Day 99
Day 113	–	FU-WK4	Day 113*#
Day 127	–	–	Day 127
Day 141	FU-WK12	–	Day 141*#
Day 148	–	–	FU-WK1
Day 155	–	–	FU-WK2
Day 169	–	FU-WK12	FU-WK4
Day 225	FU-WK24*	–	FU-WK12
Day 253	–	FU-WK24*	–
Day 309	–	–	FU-WK24*

*Weight (and the calculation of BMI) performed at this subset of the visits.

“Pre-dose” and “Post-dose” timepoints will be displayed for vital signs that were collected on injection days.

Table 3-3. Remapped Follow-Up Visits for IFNy ELISpot Assay

Nominal Visit	Cohorts 1, 2	Cohorts 3, 4, 5, 6	Cohorts 7, 8
Last Value prior to first dose date=Baseline	Baseline	Baseline	Baseline
Day 15	Day 15	Day 15	–
Day 29	Day 29	Day 29	–
Day 43	–	Day 43	–
Day 57	Day 57	Day 57	Day 57
Day 71	FU-WK2	Day 71	Day 71
Day 85	FU-WK4	Day 85	Day 85
Day 99	–	FU-WK2	Day 99
Day 113	–	FU-WK4	Day 113
Day 127	–	–	Day 127
Day 141	FU-WK12	–	Day 141
Day 155	–	–	FU-WK2
Day 169	–	FU-WK12	FU-WK4
Day 225	FU-WK24	–	FU-WK12

Table 3-4. Remapped Follow-Up Visits for ECGs

Nominal Visit	Cohorts 1, 2	Cohorts 3, 4, 5, 6	Cohorts 7, 8
Last Value prior to first dose date=Baseline	Baseline	Baseline	Baseline
Day 85	–	Day 85	Day 85
Day 141	–	–	Day 141
Day 225	FU-WK24	–	–
Day 253	–	FU-WK24	–
Day 309	–	–	FU-WK24

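### SAP 6.3.1 summarizes HBsAg change only as each participant's best decrease, so its size is biased upward and no summary shows its time course or durability

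*SAP*

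**What the plan says.** Protocol Table 7 and SAP 1.1 both list "Change in HBsAg from baseline" as an exploratory endpoint in participants with CHB. The note under the SAP table says "Only exploratory objectives to be analyzed under this SAP are included", so this endpoint belongs to this SAP rather than to the separate biomarker analysis plan.

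SAP 6.3.1 is the only place where quantitative HBsAg change is summarized. It states that the baseline value and "lowest change from baseline value after study Day 1 for each participant will be summarized"; this lowest change, in log10 IU/mL, is multiplied by -1 and presented in an 8-number summary by active cohort and pooled placebo. The same number "will be used to classify the participant's best HBsAg" response: at least 1 log10, 0.5 to below 1, or below 0.5. A second visit is not needed to confirm the class.

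Other markers are treated differently. SAP 6.3 plans a summary of "quantitative HBeAg (IU/mL) and change from baseline by visit". SAP 6.2 does the same for anti-HBs in healthy participants, and SAP 7.2.1 for selected safety laboratory tests, a list that does not include HBsAg.

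**The concern.** A best-ever decrease answers a different question from change at a given time. It picks the most favourable of several noisy differences, so its expected value is above zero in every arm even when HBsAg does not move. Read as the size of a decline, it is too large.

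It also carries no timing. A participant with one low value who returns to baseline is summarized much like one whose HBsAg falls and stays down. Protocol 1.1 itself describes a comparable therapeutic vaccine in terms of a sustained HBsAg decline, so durability is a natural question for Phase 1b, and the planned summaries cannot answer it.

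**Working it through.** The plan gives no figure for this endpoint, so there is none to reproduce.

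**Inputs**
- Baseline is a single value: "Baseline is defined as the last available value collected on or prior to the first dose date" (SAP 3.8.1).
- Postbaseline HBsAg visits are those flagged for viral biomarkers in SAP Table 3-1. Cohorts 5 and 6 have Days 15, 29, 57, 85, 113, 169 and 253, so k = 7. Cohort 7 has Days 15, 29, 57, 85, 113, 141, 169, 225 and 309, so k = 9.
- Group sizes are 8 active and 2 placebo per cohort (SAP 1.3). Pooled Phase 1b placebo is 6 people: 4 on the 7-visit schedule and 2 on the 9-visit schedule.
- The within-person SD of log10 HBsAg, σ, is not in the documents. It is assumed here, over 0.05 to 0.15.

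**Expected maximum decrease with no true change**

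With baseline B and visits Y1 to Yk, the statistic is D = B − min(Yj). With independent normal errors of SD σ, E[D] = σ × m(k), where m(k) is the expected maximum of k standard normal values: m(7) = 1.352 and m(9) = 1.485. The chance that D is positive is k/(k+1), which is 7/8 = 87.5% or 9/10 = 90%. The threshold probabilities below come from simulation (300,000 participants per scenario).

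| σ (assumed) | Mean D, 7 visits | Mean D, 9 visits | P(D ≥ 0.5), 7 visits | P(D ≥ 0.5), 9 visits |
|---|---|---|---|---|
| 0.05 | 0.07 | 0.07 | about 0 | about 0 |
| 0.10 | 0.14 | 0.15 | 0.14% | 0.17% |
| 0.15 | 0.20 | 0.22 | 4.8% | 5.8% |

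Change at one fixed visit has expectation zero under the same model. At σ = 0.15 it reaches 0.5 log10 in about 0.9% of participants.

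**Correlated visits**

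Under AR(1) correlation the shift falls but stays positive: 1.26 / 1.41 σ at 0.3, 1.08 / 1.23 σ at 0.6, and 0.84 / 0.97 σ at 0.8 (7 / 9 visits).

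**Active against placebo**

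Pooled placebo expectation: (4 × 1.352 + 2 × 1.485) / 6 = 1.396 σ. With no effect, Cohort 7 exceeds it by 1.485 − 1.396 = 0.089 σ, and Cohorts 5 and 6 fall below it by 1.396 − 1.352 = 0.044 σ. At σ = 0.10 these are about 0.009 and 0.004 log10. The standard error of an 8-versus-6 difference in D is about 0.63 σ, so the larger offset is roughly one-seventh of sampling noise.

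**Transient against sustained decline**

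This simulation uses a true 0.5 log10 fall and σ = 0.10.

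| True pattern | Mean best decrease (7 / 9 visits) | Classed ≥ 0.5 (7 / 9 visits) | Mean decrease at last visit |
|---|---|---|---|
| Dip at Day 113 only | 0.50 / 0.50 | 50% / 50% | 0.00 |
| Sustained from Day 113 | 0.59 / 0.62 | 75% / 83% | 0.50 |

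The best-decrease means differ by about 0.1 log10 between two patterns whose last-visit means differ by 0.5.

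**The case against.** The strongest reply is that the statistic is openly labelled as a maximum decrease and a best response, stands beside a placebo column with nearly the same shift, and concerns an exploratory endpoint. SAP 3.5 rules out formal testing, and the dosing decisions in SAP 2.1.1 rest on safety data. All of this stands and limits the severity.

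SAP 6.3 also promises listings of HBV serology, and SAP 3.8.1 says study day and follow-up day will appear in listings of remapped endpoints. With about 10 people per cohort, individual trajectories may be readable there. SAP 6.3.2 covers confirmed loss and reversion, but only for qualitative HBsAg loss. None of this is a summary of quantitative change over time.

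A reader might infer more than the documents support:
- *That the protocol endpoint has been abandoned, against the SAP 2.3 statement that no changes are planned.* The endpoint names no time point or summary statistic, and a maximum decrease is computed from change from baseline.
- *That real declines are likely to be no larger than the built-in shift.* Neither document states an expected HBsAg decline.
- *That the mix of 7-visit and 9-visit schedules spoils the placebo comparison.* The offset is at most about 0.09 σ.
- *That the response classes are unreliable.* False entry into the 0.5 log10 class reaches 5% to 6% only at the top of the assumed SD range. At σ = 0.10 it is 0.1% to 0.2%.
- *That every untreated participant would show a decrease.* The shift is in expectation. In the independent-error model 10% to 12.5% would show none.

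**Conclusion.** The concern holds in limited form. The only planned summary of quantitative HBsAg change is a best-of-7 or best-of-9 value and unconfirmed classes derived from it. Under no true change and independent errors it overstates the absolute decline by about 1.35 σ or 1.49 σ on average, and by 0.84 σ or 0.97 σ if visits are correlated at AR(1) 0.8. In log10 units this depends wholly on an SD the documents do not give.

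The missing summary of time course and durability does not depend on that SD. The active-placebo contrast is close to unaffected. Severity is low: the primary and secondary endpoints are untouched, and the correction is almost free.

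**What to change.** Add to SAP 6.3.1 an 8-number summary of log10 HBsAg and its change from baseline at each viral-biomarker visit in Table 3-1, through FU-WK4, FU-WK12 and FU-WK24, by active cohort and pooled placebo. Keep the maximum decrease and its classes as supportive, with a footnote that the maximum is taken over 7 or 9 visits and is expected to exceed zero without any effect.

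The cost is one additional table. The values are already collected and mapped to visits: Table 3-1 notes "Viral biomarkers (HBV DNA, quantitative HBsAg, anti-HBsAg antibody, HBcrAg, HBeAg and anti-HBeAg antibody) collected at this subset of visits". No new sample, visit or participant is needed.

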6.3.2. HBsAg Serology Results

A summary table will be provided for HBsAg-related serology results for participants on active treatment within each cohort (5, 6, and 7), and for all CHB participants assigned to placebo for the FAS (participants with HBsAg positive at baseline). The proportion of participants who have ever had HBsAg loss, confirmed HBsAg loss, HBsAg loss with HBsAb seroconversion, HBsAg loss with HBsAb seroreversion, and HBsAg loss reversion with or without HBsAb seroconversion will be summarized.

HBV serology definitions:

- **HBsAg loss:** HBsAg changing from positive at baseline to negative at any postbaseline visit.
- **Confirmed HBsAg loss:** HBsAg loss confirmed by any 2 consecutive results.
- **HBsAg loss reversion:** Any postbaseline HBsAg positive result following HBsAg loss.
- **HBsAb seroconversion:** HBsAb changing from negative or missing at baseline to positive at any postbaseline visit.
- **Confirmed HBsAb seroconversion:** HBsAb changing from negative or missing at baseline to positive at any postbaseline visit confirmed by any 2 consecutive results.
- **HBsAb seroreversion:** Any postbaseline HBsAb negative result following HBsAb seroconversion.

Both baseline and postbaseline borderline results for HBeAg, HBeAb, HBsAg, and HBsAb will be imputed as follows:

- HBsAg and HBeAg results reported as “Equivocal” will be considered HBsAg positive and HBeAg positive, respectively. HBsAb and HBeAb reported as “Equivocal” will be considered HBsAb negative and HBeAb negative, respectively for purposes of analysis
- HBsAg result reported as “Positive Confirmed” will be considered HBsAg “Positive”

Missing data will be treated as a nonevent unless otherwise specified (eg, no HBsAg loss, no seroconversion, etc.)

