6.3.3. HBeAg Serology Results

A summary table will be provided for HBeAg-related serology results for participants on active treatment within each cohort (5, 6, and 7), and for all CHB participants assigned to placebo for the FAS (participants with HBeAg positive at baseline). The proportion of participants who have ever had HBeAg loss, confirmed HBeAg loss, HBeAg loss with HBeAb seroconversion, HBeAg loss with HBeAb seroreversion, and HBeAg loss reversion with or without HBeAb seroconversion will be summarized.

HBeAg-related terminology is defined similarly to the HBsAg-related terminology.

No statistical testing is planned.

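### The reversion and seroreversion rows in SAP 6.3.2 (and, by inference, 6.3.3) can understate reversion, because anyone with no result after loss or seroconversion is counted as not reverting

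*SAP*

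**What the plan says.** SAP 6.3.2 plans one table by treatment group with rows for HBsAg loss, confirmed loss, loss with HBsAb seroconversion, loss with HBsAb seroreversion, and loss reversion. The relevant texts are:

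- Population: "for the FAS (participants with HBsAg positive at baseline". No other denominator is given for any row.
- Loss: "HBsAg changing from positive at baseline to negative at any postbaseline visit". A single negative is enough.
- Confirmed loss: "HBsAg loss confirmed by any 2 consecutive results".
- Loss reversion: "Any postbaseline HBsAg positive result following HBsAg loss".
- Seroreversion: "Any postbaseline HBsAb negative result following HBsAb seroconversion".
- Missing data: "Missing data will be treated as a nonevent unless otherwise specified (eg, no HBsAg loss, no seroconversion, etc".

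Confirmed seroconversion is defined in the same section but is not among the listed rows.

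SAP 6.3.3 plans the matching HBeAg table "for the FAS (participants with HBeAg positive at baseline" and states: "HBeAg-related terminology is defined similarly to the HBsAg-related terminology". It does not restate the missing-data rule. The general rule in SAP 3.6.1 is no imputation unless a method is specified. SAP 6.3 also plans listings of HBV serology for the Phase 1b participants.

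**The concern.** Counting missing as a nonevent is conservative when the event is favourable: a participant with no result gets no credit for loss or seroconversion. When the event is unfavourable, the same convention works in the favourable direction, because a participant who was not looked at again is scored as not having reverted. The rule's two examples are both favourable outcomes, followed by an open-ended et cetera, and nothing excludes reversion or seroreversion.

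The denominator adds to this. A participant who never lost the antigen cannot revert, yet stays in the denominator. A participant who lost it and was never retested is in the denominator and cannot be in the numerator. The table plans no count of such participants.

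At stake is how any HBsAg or HBeAg loss is read. Protocol 1.1 links the value of HBsAg loss to the chance of viral rebound, and Protocol Table 7 lists HBsAg loss with or without seroconversion as an exploratory endpoint.

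**Working it through.** The plan states no figure on this point, so there is none to reproduce. The check sets the definitions side by side and adds simple counts.

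**Inputs.** Eight active and two placebo participants per cohort (SAP 1.3), so the three CHB cohorts have 24 active and 6 placebo, 30 in all. Postbaseline viral-biomarker visits (SAP Table 3-1) are Days 15, 29, 57, 85, 113, 169 and 253 in Cohorts 5 and 6 (7 visits), and Days 15, 29, 57, 85, 113, 141, 169, 225 and 309 in Cohort 7 (9 visits). The background HBsAg loss rate is 0.5% to 1.0% per year (Protocol 1.2.3).

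**Step 1: how each result pattern is scored.** All patterns start from positive at baseline.

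| Pattern after baseline | Loss | Confirmed loss | Reversion |
|---|---|---|---|
| A: negative, nothing later | yes | no | no |
| B: negative, then positive, nothing later | yes | no | yes |
| C: negative twice, nothing later | yes | yes | no |
| D: negative twice, then positive | yes | yes | yes |
| E: negative at every later visit to the end (at least two negatives) | yes | yes | no |

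C and E are scored alike, although E has longer observed persistence. A differs from E only in the confirmed-loss row. The row totals do not always give the number of A participants: three losses made up of A, B and C, or of A, A and D, both show loss 3, confirmed loss 1, reversion 1.

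**Step 2: size in one active group of 8 (assumed counts, all positive at baseline).**

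| Losses | No later result | Observed reversions | SAP row | Among those with a later result | If all unobserved had reverted |
|---|---|---|---|---|---|
| 1 | 1 | 0 | 0/8 = 0% | 0/0, not estimable | 1/8 = 12.5% |
| 2 | 1 | 1 | 1/8 = 12.5% | 1/1 | 2/8 = 25% |
| 3 | 1 | 1 | 1/8 = 12.5% | 1/2 | 2/8 = 25% |
| 3 | 2 | 1 | 1/8 = 12.5% | 1/1 | 3/8 = 37.5% |

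The last two lines are the two mixes from Step 1. The SAP row is the same for both.

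**Step 3: losses first seen at the last visit.** No viral-biomarker visit is scheduled after Day 253 or Day 309, so this does not depend on dropout. The documents do not give the timing of loss, so two assumptions are shown.

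- First loss equally likely at each visit: 1/7 = 14% (Cohorts 5 and 6), 1/9 = 11% (Cohort 7).
- First loss uniform over time, with a last interval of 253 − 169 = 84 or 309 − 225 = 84 days: 84/252 = 33% and 84/308 = 27%.

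**Step 4: how many losses to expect without a vaccine effect.** Follow-up is (20 × 253 + 10 × 309)/365.25 = 22.3 person-years. At annual rate r, expected losses are 20 × [1 − (1 − r)^(253/365.25)] + 10 × [1 − (1 − r)^(309/365.25)].

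- r = 0.5%: 0.11 losses, 11% chance of at least one.
- r = 1.0%: 0.22 losses, 20% chance of at least one.

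The HBeAg table cannot be sized, because the number HBeAg positive at baseline is not given.

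**The case against.** The strongest reply is that the missing-data rule is not what drives the result. Reversion and seroreversion are defined by an observed later result, and SAP 3.6.1 imputes nothing by default, so a participant with no later result would go uncounted even without the rule. That stands: narrowing the rule alone changes no count. What changes the reading is the denominator and the count of those not evaluable.

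Second, a reader might infer that a loss never retested is presented as durable, or that reversion is the only planned information on durability. The documents do not support either. A never-retested loss appears under loss but not under confirmed loss, and the serology listings let each participant be followed individually. Two gaps remain: a participant whose last result is the confirming negative still counts as not reverted, and the seroreversion row has no confirmed-seroconversion row beside it.

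Third, a loss first seen at the last visit is end of follow-up rather than missing data. That is right as a matter of terms, but the row scores it in the same way.

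Fourth, a reader might infer that dropout will commonly flatter the rows. The protocol asks sites to keep participants in follow-up after they stop dosing (6.6) and draws viral biomarkers at the early termination visit (Tables 2 and 3), so the extent is unknown and may be small. A first loss at an early termination visit that ends participation still has no retest.

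Fifth, a common denominator keeps rows comparable. That is a good reason to keep the FAS rows and add to them.

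**Conclusion.** The point holds as a minor one. As written, the reversion and seroreversion rows can understate reversion, because participants with no result after the qualifying event are counted as not reverting and are not shown separately. For seroreversion the preceding event is antibody seroconversion; antigen loss comes in only because the row is restricted to participants with loss. Extension to HBeAg is an inference: SAP 6.3.3 carries over terminology and uses the same kind of population without repeating the rule, although the equivocal-result conventions in 6.3.2 already name HBeAg and HBeAb.

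The practical size is one or two participants in a table, each worth 12.5 points in an active group of 8. The shares of 14% and 11% (or 33% and 27%) are illustrations that rest on the assumed timing of first loss, and the counts in Step 2 are assumed. Without a vaccine effect the HBsAg rows will probably be empty. The analysis is exploratory and descriptive, with no testing, so no primary or secondary conclusion is affected.

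**What to change.** In SAP 6.3.2, and explicitly in 6.3.3:

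1. State that missing counts as a nonevent for loss and seroconversion only.
2. Keep the existing rows on baseline-positive FAS participants, for comparability.
3. Add reversion as n/N among participants with loss and at least one later antigen result, and seroreversion as n/N among those with seroconversion (and with loss, as the row is framed) and at least one later antibody result.
4. Beside each, show the number not evaluable after the event.

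In item 3 the confirming negative counts as a later result. To bring out participants whose last result is that confirming negative, the same two figures can be given with confirmed loss as the qualifying event and only results after confirmation counted.

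The cost is SAP wording and a few extra rows in two tables, from data already collected. The drawback is very small denominators, where one participant can move a figure from 0% to 100%, so these rows should be reported as n/N and not as percentages alone.
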